2.3.2 Determination of sample size

The primary objective is not to formally demonstrate the superiority of PRM-151 over placebo, but to provide a reliable estimate of the size of the effect of PRM-151 on absolute change from baseline to 28 weeks in mean FVC [% predicted], hereafter referred to as the primary endpoint. Nevertheless, the sample-size has been calculated to ensure a sufficient power to demonstrate the efficacy of PRM-151 over placebo on the primary endpoint under a set of hypotheses on effect sizes in the two groups and on the variability of the primary endpoint. The primary endpoint will be tested in a model with two types of subjects: subjects on a stable dose of pirfenidone or nintedanib, and subjects not on other treatment for IPF. The sample size calculation is based on the following assumptions:

- Primary endpoint is normally distributed.
- Homogeneity of variance, *i.e.*, the standard deviation is the same in both arms, and for both types of subjects.
- Randomization ratio PRM-151: placebo equals 2:1.
- Expected value of the primary endpoint for subjects on pirfenidone or nintedanib will be -1.5%.
- Expected value of the primary endpoint for subjects on no other treatment will be -3%.
- Expected value of the primary endpoint for subjects on PRM-151 will be $\geq 0.75\%$.
- Standard deviation of the primary endpoint is 5%.
- 75% of subjects will be on a stable dose of pirfenidone or nintedanib.
- 25% of subjects will not be on other treatment for IPF.
- Significance level (α)=0.10 two-sided.
- Desired power to demonstrate superiority is 80%.

A sample size of one hundred and two (102) evaluable subjects in total (68 PRM-151 and 34 placebo) is enough to demonstrate statistical significance at $p < 0.10$ two-sided with a power of 80% under the above assumptions. Assuming a non-evaluability rate of about 15%, 117 subjects in total (78 PRM-151 and 39 placebo) are to be enrolled. Stratified randomization will ensure a balance of PRM-151: placebo within patients on pirfenidone or nintedanib and not on any other therapy, with at least 25% of patients on no other therapy.

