5.2.5 Efficacy Analysis

5.2.5.1 Primary endpoint analysis

Primary efficacy analysis

Descriptive statistics for (i) raw values at each time point and (ii) change from baseline to each time point in FVC [% predicted] will be computed by treatment group for the ATS analysis dataset (Statistical tables 14.2.1.1.1 and 14.2.1.2.1). The time variation in FVC [% predicted] will be modelled using a linear mixed effect model with random intercept, with raw values at each time point (from Week 4 to Week 28 included) in FVC [% predicted] as dependent variable (outcome), and stratum, treatment, time (continuous variable calculated as the actual number of days since baseline) and treatment by time interaction as explanatory variables (Statistical table 14.2.1.3.1).

The following statistical hypotheses will be tested:

- H0: Absence of difference between the treatment groups.
- H1: A difference exists between the treatment groups.

Least square means for FVC [% predicted] at each time-point (Statistical table 14.2.1.3.1, Figure 14.2.1.1), estimate of slopes, together with their 2-sided 90 and 95% confidence intervals will be presented for both treatment groups.

The comparison of PRM-151 with placebo will be carried out by

1. computing the estimate (estimate statement from SAS Proc MIXED) of the between group difference in change from baseline at week 28,
2. computing the corresponding 90% confidence interval
3. computing the p-value of the difference estimate compared to 0.

Statistical significance will be determined using a 2-sided type-one error rate of 0.10.

The listing of the estimates of the random parameters will be provided (Listing 16.2.6.9.1)

Due to the number of sites planned to recruit and randomize patients in the study, it is expected that each site will include too few patients to allow the inclusion of study site as a covariate in the analysis.

Sensitivity efficacy analysis on the Full Analysis Set population

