To assess the effect of including or excluding patient without any post-baseline efficacy measurement from the primary efficacy analysis population (ATS), the primary efficacy analysis described above will be repeated on the Full analysis set population (initially planned in the protocol as the primary efficacy population) and defined as all randomized patients having received at least one administration of the study medication with a baseline and at least one post-baseline assessment of FVC [% predicted] (primary efficacy criterion) available (Statistical tables 14.2.1.1.3, 14.2.1.2.3 and 14.2.1.3.3, Figure 14.2.1.3)

Sensitivity efficacy analysis on the ATS dataset

The primary efficacy analysis as described above will be repeated with addition of descriptive statistics by stratum, and of the treatment by stratum by time interaction, together with the three two by two interactions, terms in the analysis model (Statistical tables 14.2.2.1, 14.2.2.2, 14.2.2.3, Figure 14.2.2).

In case of a significant qualitative treatment by stratum by time interaction, the data will be carefully examined searching for a potential explanation and the conclusions of the primary efficacy analysis will have to be interpreted cautiously.

The primary efficacy analysis as described above will be repeated without adjusting on stratum in the analysis model (Statistical table 14.2.3).

Potential differences in treatment effect according to study site will be addressed by tabulating both raw values of FVC [% predicted] and change from baseline to each visit in FVC [% predicted] by site on the ATS (Statistical tables 14.2.4.1.1 and 14.2.4.2.18), but it is expected that due to the small number of patients within each site no precise estimates will be obtained for most of the sites.

Sensitivity efficacy analysis on the PP dataset

The primary efficacy analysis as described above will be repeated on the PP analysis data set (Statistical tables 14.2.1.1.2, 14.2.1.2.2 and 14.2.1.3.2, Figure 14.2.1.2).

Initially planned primary efficacy analysis (ATS and FAS)

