5.3 Statistical/Analytical issues

5.3.1 Adjustments for Covariates

All comparisons of change from baseline to a given visit between treatment groups performed using ANOVA models and pooling subjects on a stable dose of pirfenidone or nintedanib with subjects not on other treatment for IPF, are adjusted for stratification levels.

Analysis of time variation in a given variable using Linear Mixed Models and pooling subjects on a stable dose of pirfenidone or nintedanib with subjects not on other treatment for IPF, are all adjusted for baseline measurements of the response variable and stratification levels.

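### As listed, the primary mixed model gives the Week 28 difference in change almost no stratum adjustment, so the planned repeat without stratum is nearly the same analysis

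*SAP*

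**What the plan says.** - **Primary model (SAP 5.2.5.1).** The outcome is raw FVC % predicted at the visits from Week 4 to Week 28, with a random intercept "and stratum, treatment, time (continuous variable calculated as the actual number of days since baseline) and treatment by time interaction as explanatory variables". The test concerns the difference between arms in change at Week 28, obtained from an SAS estimate statement whose coefficients are not given.
- **Sensitivity analyses (SAP 5.2.5.1).** "The primary efficacy analysis as described above will be repeated without adjusting on stratum in the analysis model". Another run adds the three-way interaction and all two-way terms, so it contains stratum by time. The protocol's ANOVA of change on treatment and stratum is kept on both the ATS and the FAS, with multiple imputation.
- **Covariates (SAP 5.3.1).** Pooled mixed models "are all adjusted for baseline measurements of the response variable and stratification levels". The list in 5.2.5.1 has no baseline term.
- **Protocol 8.5.1.1.** The primary analysis was an ANOVA with change as the outcome and treatment and stratum as factors. SAP 6.1 announces the move to a mixed model but does not say what happens to the stratum adjustment.
- **Planning assumptions (SAP 2.3.2).** "Expected value of the primary endpoint for subjects on no other treatment will be -3", against -1.5 for subjects on pirfenidone or nintedanib.

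**The concern.** When the outcome is change, a stratum factor adjusts change. When the outcome is the raw level over time, a stratum main effect adjusts only the level, and the random intercept already takes up level differences between subjects. The SAP kept the same term while changing the outcome, so most of the adjustment was lost without comment.

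Two things are at stake. First, the one analysis from which efficacy conclusions are drawn would not adjust its contrast for the randomisation stratum, although 5.3.1 says that it does and the plan expects the strata to change at different rates. Second, the run without stratum would be reported as a robustness check when its agreement with the primary result is largely built in.

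**Working it through.** **1. The plan's own figure.** Inputs from SAP 2.3.2: alpha "0.10 two-sided"; "Desired power to demonstrate superiority is 80" (per cent); "Randomization ratio PRM-151: placebo equals 2:1"; SD 5; stratum mix 75/25; placebo changes -1.5 and -3; PRM-151 change 0.75.

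- Pooled effect = 0.75 × (0.75 + 1.5) + 0.25 × (0.75 + 3) = 1.6875 + 0.9375 = 2.625.
- Placebo n = (1.645 + 0.842)² × 25 × (1 + 1/2) / 2.625² = 33.7, so 34; with 68 on PRM-151 the total is 102. Power at 68/34 is 80.4%.

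The figure of 102 reproduces, and nothing below changes it.

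**2. The contrast.** Write the listed model as

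E(FVC) = b0 + b1·stratum + b2·treatment + b3·day + b4·treatment·day, plus a subject intercept.

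Modelled change from Day 0 to Day 196 is 196·(b3 + b4·treatment), so the difference between arms is 196·b4. The coefficient b1 has dropped out. With complete data at common times, the estimate of b4 is the difference between arms in mean within-subject slope, and stratum cannot alter it. With actual days and missing visits, a little between-subject information enters b4, so stratum has a small influence.

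**3. Size.** Simulations used 117 subjects (58/29 and 20/10 by stratum), seven visits, the plan's stratum-specific changes, SD of change 5, and REML random-intercept fits. Assumptions that are not in the documents: residual SD 2.5; baseline mean 70 and SD 11; a stratum difference in FVC level of 0 or 5 points; 15% dropout with 3% missed visits, or 30% and 10% as a stress case. Decisions use the SAP rule: "Statistical significance will be determined using a 2-sided type-one error rate of 0.10". Shifts are absolute, in points of FVC % predicted.

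| Scenario (slope contrast, no baseline term) | Dropping stratum: mean, max | Adding stratum by time: mean, max | Decisions changed by adding |
|---|---|---|---|
| Complete, on schedule, balanced | rounding error (about 1e-11) | rounding error | 0 |
| 15% dropout, ±3-day visits, balanced | 0.002–0.004, 0.026 | 0.024–0.025, 0.24 | 0.5% |
| 30% dropout (stress case), balanced | 0.007, 0.036 | 0.037, 0.30 | 1.0% |
| Assumed imbalance (62/25 and 16/14), complete | rounding error | 0.150, 0.70 | 2.3% |
| Same imbalance, 15% dropout | 0.005, 0.033 | 0.158, 0.61 | 2.2% |

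Dropping stratum changed no decision in any row except the stress case (0.1%). Under balance the mean model SE is the same with or without stratum by time (0.707 and 0.706 with complete data; 0.76 with dropout). Under the assumed imbalance it rises by 0.01.

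**4. Differential dropout.** A further simulation (102 patients, 1,500 trials) assumed that 40% of placebo patients without background therapy leave after Week 8 to 12, against 10% of everyone else. Adding stratum by time moved the estimate by 0.077 on average, with a 95th percentile of 0.233 (0.233 / 2.625 = 9%). The mean estimate went from 2.519 to 2.545, a shift of 0.026 or 1% of 2.625.

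**5. The other reading of the contrast.** If baseline is a covariate, as 5.3.1 says, and the contrast is the difference at Day 196, the stratum main effect does adjust. Dropping it then moves the estimate by 0.006 to 0.010 on average (maximum 0.09) with 15% dropout and balance, and by 0.11 (maximum 0.52) under the assumed imbalance with dropout.

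**The case against.** A reader might infer that stratum is wholly inert and that the no-stratum run must return the primary result. The documents do not support that. Exact identity needs complete data at common times, whereas the SAP uses actual days and leaves missing values unimputed.

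Nor can 5.3.1 be called plainly false. The contrast coefficients are unstated, and the protocol's own repeated-measures model (8.5.1.3.2) has baseline as a covariate beside a stratum main effect. Under that reading with a Day 196 contrast, stratum does adjust. This stands, and it means that the contradiction between 5.2.5.1 and 5.3.1 has to be settled. It does not rescue the model as 5.2.5.1 lists it, and adding baseline while keeping a slope contrast would not restore the adjustment.

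A reader might also infer material bias, citing the 9% figure. That is a 95th percentile under an assumed dropout pattern; the documents give only a non-evaluable rate of about 15%. The cell concerned holds about 102 × 0.25 / 3 = 8.5 patients, so the scenario turns on three or four of them leaving.

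Two further points stand. The planned -1.5 and -3 differ on the placebo side only, since PRM-151 is assumed to give at least 0.75 without a split by stratum. That is a three-way pattern which an additive stratum-by-time term captures only on average. And the retained ANOVA on change and the full-interaction model already show stratum-adjusted results, although only as sensitivity analyses, and for the interaction model no stratum weighting for a single pooled contrast is stated.

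**Conclusion.** The point holds as a specification defect of minor severity. As 5.2.5.1 is written, the Week 28 difference in change receives almost no adjustment for the randomisation stratum, contrary to 5.3.1 and unlike the protocol's ANOVA, and the no-stratum repeat is too close to the primary analysis to count as a robustness check.

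The expected effect on the estimate is about 0.02 points under 2:1 balance within strata and ordinary dropout. Larger shifts appear only under assumed differential dropout (0.08 on average) or assumed imbalance of arms across strata (about 0.15). All of these rest on the slope reading of the contrast and on the variance and dropout assumptions stated above. One caution on the decision rates: the simulations let slopes vary between subjects, so the random-intercept SE (0.76) was below the empirical SD of the estimate (1.02). That is a separate matter from this point.

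**What to change.** - Add stratum by time to the primary model in SAP 5.2.5.1 and to the pooled models with repeated post-baseline visits: FVC, 6MWD, K-BILD and LCQ. Do not add it to models fitted within one stratum or one background drug, where it does not exist, or to HRCT and DLCO, whose only post-baseline visit in the randomised phase is Week 28.
- Redefine the no-stratum sensitivity analysis as removing both stratum and stratum by time, or delete it.
- Write out the estimate-statement contrast: either 196 times the treatment-by-time coefficient, or the Day 196 difference with baseline in the model.
- Make 5.2.5.1 and 5.3.1 agree on whether baseline is a covariate, and record in 6.1 how stratum is handled in the new model.

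The cost is one degree of freedom per model and a few lines of SAP text before database lock. Precision is unchanged under the planned balance, and the sample size stays at 102 evaluable subjects.

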3.2 Primary efficacy dataset: All Treated Set (ATS)

The All Treated Set (ATS) will consist of all randomized patients having received at least one administration of the study medication. The patients will be analyzed in the treatment arm attributed by the randomization process whatever the treatment they actually received (“as randomized” analysis).

The ATS dataset will be used for the primary efficacy analyses in this trial.

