5.3.2 Handling of Dropouts or Missing Data

Missing data in efficacy analysis:

The statistical model (linear mixed models for repeated measures) used for the primary and most secondary efficacy analyses will be used without imputation of missing values and are valid under the assumption of missingness at random.

Multiple imputation techniques will be used for the sensitivity analysis on the initially planned primary analysis (see Section 5.2.5.1).

All available efficacy and safety data will be included in data listings and tabulations.

Missing or incomplete dates:

For all listings, missing or incomplete dates will be left as they were recorded.

For calculation / sorting / assignment based on dates (*e.g.*, treatment emergent AEs, concomitant medications...), the following rules will apply:

- The most conservative approach will be considered (*i.e.*, if the onset date of an AE/concomitant medication is missing / incomplete, it will be assumed to have occurred during the study treatment phase (*i.e.*, a TEAE for AEs) except when the partial onset date or other available data indicates differently (*e.g.*, start date day missing, but month before the month of baseline date, or stop date before baseline date).
- Medical history or disease diagnosis with missing/incomplete date will be assumed to have occurred before any study treatment except when the partial onset date or other available data indicates differently.
- Assignations based on dates will be reviewed and confirmed or infirmed during the data review meeting
- Missing or partial start or end dates of IMP administration, if any, will be reviewed during the data review meeting.

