5.3.6 Use of an "Efficacy Subset" of Patients

Two efficacy analyses populations are defined, the ATS and the PP. The definition of these populations is available in Section 3. The primary efficacy analysis will be conducted on the ATS. No patient with available post-treatment efficacy data are excluded from the ATS and, consequently from the primary efficacy analysis.

The PP population will be used to conduct a sensitivity analysis and assess the robustness of the primary efficacy analysis conclusions. Any substantial difference between the two analyses will be explored and discussed.

In addition, the SAP planned to conduct the primary analysis on the Full analysis Set. This was then changed to the ATS. Nevertheless, the initially planned analysis on the FAS will be conducted and provided as an additional sensitivity analysis to further assess the robustness of the primary efficacy analysis conclusions and in particular to assess the impact of excluding patient without any post-baseline efficacy measurement from the FASATS population. Any substantial difference with the result obtained for the primary efficacy analysis on the ATS will be explored and discussed.

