6.1 Change in the primary efficacy analysis

According to the protocol, the primary efficacy analysis was to be the Full Analysis Set (FAS), defined as all randomized patients having received at least one administration of the study medication with a baseline and at least one post-baseline assessment of FVC [% predicted] (primary efficacy criterion) available.

Limiting the population to subjects having at least one post-baseline assessment of FVC [% predicted] draws the efficacy population further from the intention to treat paradigm than the exclusion of only untreated patients. Consequently, it has been decided to change the primary efficacy analysis population to the All Treated Set (ATS, see section 3.2) defined as all randomized subjects who have received at least one administration of the investigational medicinal product (IMP).

In addition to this change of population, it has been decided to change the analysis model from the initially planned ANOVA model on change from baseline to week 28 to a linear mixed effect model with random intercept using all measurements available until Week 28 used to compute the estimate of the between group difference in change from baseline at week 28.

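### The FAS repeat of the primary mixed model uses the same rows as the ATS primary, so it cannot test the exclusion of patients without post-baseline FVC

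*SAP*

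**What the plan says.** SAP 3.2 defines the primary efficacy set without any FVC requirement: "The All Treated Set (ATS) will consist of all randomized patients having received at least one administration of the study medication". The FAS, as restated in SAP 5.2.5.1, contains the same patients but only those "with a baseline and at least one post-baseline assessment of FVC [% predicted] (primary efficacy criterion) available".

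The primary model in SAP 5.2.5.1 is a linear mixed model with a random intercept, "with raw values at each time point (from Week 4 to Week 28 included) in FVC [% predicted] as dependent variable (outcome", and with stratum, treatment, time and treatment by time as explanatory variables. SAP 5.3.2 adds that the mixed models "will be used without imputation of missing values and are valid under the assumption of missingness at random".

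SAP 5.2.5.1 then says that "the primary efficacy analysis described above will be repeated on the Full analysis set population", with the purpose "To assess the effect of including or excluding patient without any post-baseline efficacy measurement from the primary efficacy analysis population (ATS". SAP 5.3.6 describes the FAS analysis in similar terms, "in particular to assess the impact of excluding patient without any post-baseline efficacy measurement", and promises to discuss any substantial difference. SAP 6.1 gives the reason for leaving the protocol's FAS: "Limiting the population to subjects having at least one post-baseline assessment of FVC [% predicted] draws the efficacy population further" from intention to treat than leaving out only the untreated.

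**The concern.** The patients who separate the two sets are those treated but never measured for FVC after baseline. The primary model takes in only post-baseline FVC and imputes nothing, so these patients are absent from the fit even when the set formally includes them. A comparison presented as a test of their exclusion would then compare a fit with itself.

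At stake is how the result can be read. Two matching model tables could be taken as evidence that leaving these patients out is harmless, although neither run contains them. The stated reason for changing the primary population would likewise not apply to the analysis for which the change was made.

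**Working it through.** **1. Planning figures, used only as a yardstick (SAP 2.3.2).** Placebo mean = 0.75 × (−1.5) + 0.25 × (−3) = −1.875. Effect = 0.75 − (−1.875) = 2.625. With SD 5, two-sided alpha 0.10, 80% power and 2:1 allocation, the placebo arm needs 1.5 × 25 × (1.645 + 0.842)² / 2.625² = 33.7, so 34, and 102 in total. Power at 102 is 80.4%. The plan's 102 evaluable patients reproduce and are not in dispute.

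**2. Who can be in the ATS but not in the FAS?**
- A treated patient with no FVC from Week 4 to Week 28 has no outcome row (SAP 5.2.5.1), and none is created (SAP 5.3.2). The likelihood is the same with or without that patient.
- A treated patient with post-baseline FVC but no baseline would have rows in the ATS only. SAP 5.4.1 falls back on the screening value, and eligibility itself requires an FVC, so this group is practically empty. One such simulated patient moved the estimate from 3.128 to 3.160.

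**3. Numerical check.** The model was fitted by REML to simulated data for 117 patients (78 and 39). Assumptions not in the documents: between-patient SD 11, residual SD 5/√2, linear change. Some treated patients were given no post-baseline FVC.

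| Without post-baseline FVC (PRM-151, placebo) | Week 28 contrast (SE), ATS | Same, FAS | Patients / rows in each fit |
|---|---|---|---|
| 1, 0 | 3.128 (0.933) | 3.128 (0.933) | 116 / 812 |
| 3, 2 | 3.330 (0.952) | 3.330 (0.952) | 112 / 784 |
| 6, 0 | 3.217 (0.947) | 3.217 (0.947) | 111 / 777 |
| 10, 5 | 3.543 (1.011) | 3.543 (1.011) | 102 / 714 |

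The difference is exactly zero each time. It stays zero when baseline FVC is added as a covariate, as SAP 5.3.1 says.

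**4. If baseline were an outcome row.** With six such PRM-151 patients and 60 simulations, the difference in change from baseline at Week 28 moved by −0.04 to +0.06 points between the sets, against an SE of about 0.76. The difference in FVC level at Week 28 moved more (−1.03 to +0.73), but the comparison in SAP 5.2.5.1 is on change.

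**5. The multiple-imputation ANOVA.** SAP 5.2.5.1 also runs the originally planned ANOVA on both sets with imputed Week 28 values. Here ATS and FAS can differ: 1.99 against 2.09 (five patients) and 1.94 against 1.83 (fifteen), part of which is imputation noise.

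**6. What could go unseen.** The documents give no count of these patients. Assume that each truly falls 10 points.
- PRM-151 only: loss of effect = share × (10 + 0.75). 1% gives 0.11 (4% of 2.625), 4% gives 0.43 (16%), 8% gives 0.86 (33%).
- 4% in both arms: 0.04 × 10.75 − 0.04 × (10 − 1.875) = 0.43 − 0.325 = 0.105 (4%).

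**The case against.** The strongest reply is that the SAP already brings these patients in. The multiple-imputation ANOVA is planned on both the FAS and the ATS, and the sentence in SAP 5.3.6 refers to the initially planned analysis, which may mean that ANOVA. This stands in part: a reader might infer that the SAP leaves these patients out everywhere, and that is wrong. But SAP 5.2.5.1 assigns the check explicitly to a repeat of the primary mixed model. The ANOVA is a different model, and its imputation is not described under anything other than missing at random.

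A reader might also infer that the move to the ATS achieves nothing. The documents do not support that. The protocol's FAS is defined by FVC alone (protocol 8.4), so under the ATS a patient with walk-test or questionnaire data but no post-baseline FVC can enter those analyses. The missing gain is confined to the primary FVC model.

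Third, the exact identity requires that baseline is not an outcome row. SAP 5.1.2 allows time eight levels, whereas Weeks 4 to 28 give seven visits, and SAP 6.1 speaks of all measurements up to Week 28. That doubt is fair. SAP 5.2.5.1 is explicit, however, and under the other reading the check would still move by only a few hundredths of a point.

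Finally, few such patients are likely. Protocol 5.4 calls for an End of Study visit four weeks after the last dose, and SAP 5.4.4 reallocates its data for patients who stop early. SAP 5.2.2 tabulates set sizes by arm, and descriptive tables can still differ between the sets. All this limits the consequence but does not make the FAS repeat informative.

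**Conclusion.** The point holds for the primary mixed model as SAP 5.2.5.1 writes it: the ATS and FAS runs use the same rows and give the same estimate, confidence interval and p-value. The FAS repeat cannot assess what it is said to assess, and the intention-to-treat reason in SAP 6.1 adds nothing for this model. The conclusion rests on outcome rows from Week 4 onward, no imputation, and the screening fallback for baseline.

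It does not show that the primary estimate is biased. The 0.43-point figure could be read as the expected distortion, but it is a one-arm case with an assumed share and an assumed fall. Under the same assumptions the range is 0.11 to 0.86 points for 1% to 8% in PRM-151 alone, and about 0.1 points for 4% in both arms. The defect is an empty sensitivity analysis and inaccurate wording. It should be corrected, and correcting it is cheap.

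**What to change.** - **Replace the FAS repeat** in SAP 5.2.5.1 with a sensitivity run on the ATS in which treated patients without post-baseline FVC are imputed on the placebo-arm trajectory, for example by extending the multiple imputation already planned there. Unlike the FAS repeat, this run can move: at the planning values, 4% of PRM-151 patients would shift the effect by 0.04 × 2.625 = 0.105 points. Report, per arm, how many ATS patients contribute no row to the primary model.
- **Correct the wording** in SAP 5.2.5.1, 5.3.6 and 6.1 to say that ATS and FAS coincide for the primary mixed model, and that the wider set matters for other endpoints and for the imputed ANOVA.
- **Reconcile the role of baseline FVC** across SAP 5.1.2, 5.2.5.1, 5.3.1 and 6.1: outcome row, covariate or neither. If it is to be an outcome row, that specifies the primary model itself, and the corrected wording must then say that the sets nearly coincide.

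The cost is one changed sensitivity run and SAP text, with no new data. The first two changes leave the primary estimate as it is.
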